6.1 General Safety Evaluations

A complete medical history will be obtained for the Subject's current and past medical conditions. Significant medical history should include, but not be limited to, evidence of hypertension, lipid disorders, obesity¹, heart attack, stroke, congestive heart failure, kidney disease, auto immune disease and gestational diabetes. Significant surgical history should include, but not be limited to, removal of blockage from an artery and gallbladder removal.

Concomitant medications and treatments, including the use of sunscreen, OTC products, herbal products, topical and systemic medicines, (non-drug treatments/therapies) etc., in addition to the reason for the medication use, will be assessed at screening/baseline and at each subsequent study visit. The start and stop calendar date (e.g., mm/dd/yyyy) and study day (e.g., Day X) and name of concomitant medication use during the study should be provided in the data set in addition to the reason for the medication use. It should clearly be noted whether the medication was used prior to screening/baseline visit, during the study, or both.

Additional assessment to assess subject safety, such as physical examinations, measurements of vital signs are described below and included in the Schedule of Assessments for periodic measurements.

All female subjects of childbearing potential will undergo a urine pregnancy test with a sensitivity of at least 25 mIU/ml hCG at Visit 1, Visit 2, Visit 3 and Visit 4. A negative result of urine pregnancy test at visit 1, 2, 3 and 4 should be obtained. All female subjects are considered to be of childbearing potential unless they are premenarchal or have been surgically sterilized or have been postmenopausal for at least 1 year.

6.1.1 Physical Examination

A brief physical examination will be performed at screening/baseline, Visit 4 End of Treatment/Early Discontinuation and during an UNS visit where applicable. The physical examination will include, at a minimum, examination of the Subject's general appearance, skin, HEENT (head, eyes, ears, nose and throat), heart, lungs, musculoskeletal system, neurological system, lymph nodes, abdomen and extremities. It is recommended the Subject's body weight should be measured while the Subject is lightly clothed (e.g., no coat or shoes).

The investigator, sub-investigator or appropriately delegated designee (Physician's Assistant, Advanced Registered Nurse Practitioner, and Registered Nurse as per local regulations) will perform a brief physical examination, prior to the Subject starting study drug. A delegation log will be maintained at site.

¹ Obesity = BMI \geq 30 (as defined by Metropolitan Life Insurance Company Chart, Appendix III)

6.1.2 Vital Signs

Vital signs, including blood pressure, pulse rate, respiratory rate and body temperature will be documented at Visit 1, Visit 2, Visit 3 and Visit 4. Vital signs will be measured after the subject has rested in a seated position for about 5 minutes.

Blood pressure (millimeters of mercury [mmHg]) and heart rate (beats per minute [bpm]) will be measured during the physical examination after 5 minutes rest in sitting position. Blood pressure and heart rate will be obtained preferably using the same arm and same equipment each time. If one arm has higher blood pressure than the other, that arm should be used for further blood pressure measurements (all further blood pressure measurements should be done in the same arm).

Body temperature will be measured using FDA approved tympanic or infrared thermometer with digital display and recorded in the eCRF in degree Celsius (°C). Preferably the same method will be used each time.

Vital signs, including blood pressure, pulse rate, respiratory rate and body temperature will be documented at visit 1. Vital signs will be measured after the Subject has rested in a seated position for at least 5 minutes. Additionally, temperature will also be documented at Visit 2, 3, 4 and Unscheduled / Early Discontinuation as part of COVID-19 symptom screening.

6.1.3 Pregnancy Test

All female Subjects of childbearing potential will undergo a urine pregnancy test with a sensitivity of at least 25 mIU/ml hCG during Visit 1 and at each subsequent study visit.

All female Subjects are considered to be of childbearing potential unless they are premenarchal, have been surgically sterilized (by *hysterectomy or bilateral oophorectomy) or have been postmenopausal for at least 1 year. Tubal ligation is not considered equivalent to female sterilization. Women with a history of tubal ligation are still considered females able to become pregnant and must complete a urine pregnancy test.

*Female subjects of childbearing potential (WOCBP) are defined as sexually mature women without prior hysterectomy, or who have had any evidence of menses in the past 12 months. However, women who have been amenorrheic for the past 12 or more months are still considered to be of childbearing potential, if the amenorrhea is possibly due to other causes, including prior chemotherapy, anti-estrogens, or ovarian suppression. Postmenopausal women (defined as women who have been amenorrheic for at least 12 consecutive months, in the appropriate age group, without other known or suspected primary cause) or women who have been sterilized surgically or who are otherwise proven sterile (i.e., total hysterectomy, or bilateral oophorectomy with surgery at least 4 weeks prior to randomization) are not considered WOCBP. Subjects who have undergone tubal ligation are NOT considered as surgically sterile.

Women of childbearing potential, in addition to having a negative urine pregnancy test, must be willing to use an acceptable form of birth control during the study from the day of the first dose

administration to 30 days after the last administration of study drug.

Female subjects who are premenarchal, surgically sterilized (by hysterectomy or bilateral oophorectomy) or postmenopausal for at least 1 year, do not require a urine pregnancy test and are not required to use an acceptable form of birth control.

Full hysterectomy or bilateral oophorectomy are considered surgically sterile. Tubal ligation is not considered equivalent to female sterilization.

For the purpose of this study the following are considered acceptable methods of birth control: oral or injectable contraceptives, contraceptive patches, medroxyprogesterone acetate (ex. Depo-Provera®) with stabilized use for at least 3 months, vaginal contraceptive (ex. etonogestrel/ethinyl estradiol vaginal ring (ex. NuvaRing®), contraceptive implant with etonogestrel or equivalent, double barrier methods (e.g., condom and spermicide), IUD, abstinence. If a subject who was abstinent becomes sexually active during the study, a 2nd acceptable method of birth control should be used and documented.

A sterile sexual partner is NOT considered an adequate form of birth control. Subjects on hormonal contraception must be stabilized on the same type for at least three months prior to enrollment in the study and must not change the method during the study.

6.2 Concomitant Medications

Concomitant medications and therapeutic treatments, including the use of sunscreen, OTC products, herbal products, topical and systemic medicines, dietary supplements and any current non-drug treatments/therapies will be assessed at the screening/baseline visit and at each subsequent study visit. The start and stop calendar date (e.g., dd/mmm/yyyy and study day (e.g., Day X) of concomitant medication use during the study should be provided in the data set in addition to the reason for the medication or treatment use. It should clearly be noted whether the medication was used prior to screening/baseline visit, during the study, or both.

A record of concomitant medications taken by the Subject is to be obtained using generic name, if known, with the corresponding indication. The medications to be recorded will include prescription and over-the-counter (OTC) medications and dietary supplements. Any therapeutic treatments during the trial should also be recorded. All medications taken on a regular basis, including acetaminophen, should be recorded.

6.3 Evaluation of Signs/Symptoms of Local Irritation/Application Site Reactions

At each study visit, beginning at Visit 1, Subjects will be evaluated for any signs and symptoms of local irritation such as erythema, dryness, burning/stinging, erosion, edema, pain and itching. The scores for each visit will be documented to allow a comparison between treatment groups.

The following scale will be used for the signs and symptoms of local irritation:

Score	Assessment	Description
0	Absent	None
1	Mild	Slight, barely perceptible
2	Moderate	Distinct presence
3	Severe	Marked, intense

Subjects with a screening/baseline irritation score of 3 (severe, marked/intense) will not be enrolled.

Signs and symptoms of local irritation are to be recorded only as AEs if they significantly worsen, require any medical intervention or result in subject discontinuation (eg. after screening/baseline, severe irritation (i.e., grade 3, described as severe or marked/intense) that requires treatment will be reported as an adverse event).

Local irritation reactions in the treatment area are common and the Investigator may instruct Subjects to stop the application of treatment (“rest period”) to reduce Subject discomfort and to allow local skin reactions to subside based upon the Investigator’s clinical assessment. The Investigator may advise the subject to use the Sponsor provided moisturizer at this time. Treatment should resume as soon as the reaction subsides sufficiently to allow reapplication. The [REDACTED]. The Subject should not modify or resume the treatment regimen without consultation with the Investigator. The Investigator may make this decision based upon a documented phone consultation or at an unscheduled visit. All dose modifications must be reported on the appropriate Study Medication Log & Dosing Compliance eCRF, along with Subject documenting in the subject diary.

The treatment period should not be extended beyond 12 weeks due to missed doses or rest periods. Subjects whose condition worsens or lesions do not respond to treatment following at least 28 days (or in the opinion of the Investigator) should be re-evaluated by the Investigator and management reconsidered.

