8.5 Unscheduled Visits and Early Discontinuation Visit

An Unscheduled Visit is allowed at any time, for any reason, if in the Principal Investigator's opinion, it is warranted. If the Unscheduled Visit is due to an AE, the Principal Investigator will determine whether additional visits are needed.

If a Subject is discontinued from the study during an Unscheduled Visit, the Unscheduled Visit will be referred to as an Early Discontinuation Visit and all procedures scheduled for the Early Discontinuation Visit will be performed. If the Unscheduled Visit is not an Early Discontinuation Visit (i.e., the Subject will continue to take part in the study), then the reason for the unscheduled visit is documented and required procedures at the discretion of Investigator considering the reason for visit will be performed apart from the collection of IMP and Subject diaries from Subjects.

If the Subject's condition has worsened to the degree that it is unsafe for the Subject to continue in the study, the Subject may be discontinued from the study as treatment failure and a standard of care treatment may be advised at the Principal Investigator's discretion.

[figure not shown]

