Worsening of the disease under study will be measured by an increase in the IGA score by one or more grades, and should be recorded as an adverse event only if the presentation and/or outcome is more severe than would normally be expected from the normal course of the disease in a particular subject.

In this study, any adverse event occurring after the subject has signed the informed consent/assent form until the end of follow-up period should be recorded and reported as an adverse event.

A treatment-emergent AE (TEAE) is any AE that occurs after initiation of study medication, or any event already present that worsens in either intensity or frequency following exposure to study medication.

For adverse event recording, the study period is defined for each subject as that time period from signature of the informed consent/assent form through the end of the study (including the follow up period). All adverse events that occur during the defined study period must be recorded on the source documentation and CRF, regardless of the severity of the event or judged relationship to the study drug. For serious adverse events, the Serious Adverse Event Form must also be completed, and the serious adverse event must be reported immediately (see Section on Reporting below).

At each contact with the subject, the Investigator or designee must question the subject about adverse events by asking an open-ended question such as, “Have you had any unusual symptoms or medical problems since the last visit? If yes, please describe.” All reported or observed signs and symptoms will be recorded individually, except when considered manifestations of a medical condition or disease state. A precise diagnosis will be recorded whenever possible. When such a diagnosis is made, all related signs, symptoms, and any test findings may be recorded collectively as a single diagnosis on the CRF and, if it is a serious adverse event, also on the Serious Adverse Event Form.

The onset and end dates and times, action taken regarding study drug, treatment administered, and outcome for each adverse event must be recorded on the source documentation.

The relationship of each adverse event to study drug treatment, and the severity and seriousness of each adverse event, as judged by the Investigator, must be recorded as described below.

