7.7 Safety Analyses

7.7.1 Adverse Events

Adverse Events will be coded using the MedDRA version 25.0 AE coding system for purposes of summarization.

Only treatment-emergent adverse events (TEAEs) will be used for the summary analysis. An AE will be considered as treatment-emergent if the date of onset is on or after the date of the first study medication administration or if it increased in severity during the study treatment period. AEs with unknown start dates will be counted as treatment-emergent unless the AE resolution date is prior to the study drug start date. If the AE start date is partially missing, the

AE will be considered treatment-emergent, unless the month and year (when available) rule out the possibility that the event occurred post start of the study drug.

AE will be considered treatment-related if its relationship to study product is recorded as Possible, Probable or Definitely related. AEs with missing relationship will also be considered related.

An overall summary will include, by treatment group and overall, the number of TEAEs and the number and percentage of subjects reporting at least 1 TEAE in the following categories:

- Any AE
- Any TEAE,
- Treatment-related TEAE,
- Serious TEAE,
- TEAE leading to discontinuation of the study medication.
- Fatal AE

Count of AEs by severity and relationship to the study medication will also be presented.

The following TEAE frequency tables will be prepared summarizing the number and percentage of subjects reporting at least one TEAE by MedDRA system organ class (SOC) and preferred term (PT):

- All TEAEs
- Treatment-related TEAEs
- Serious TEAEs
- TEAE leading to discontinuation of the study medication
- TEAEs by maximum severity

A subject experiencing the same AE multiple times will only be counted once for that preferred term. Similarly, if a subject experiences multiple AEs within the same system organ class, that subject will be counted only once in that system organ class. In the summary by severity only the highest applicable severity will be chosen for each preferred term and system organ class.

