7.7.4 Signs/Symptoms of Local Irritation

At each study visit, beginning with Visit 1, subjects will be evaluated for any signs and symptoms of local irritation (application site reactions), including erythema, dryness, burning/stinging, erosion, edema, pain and itching. Each subject will be assigned a severity score by an Investigator based on the scale ranging from 0=Absent to 3=Severe.

Number and percentage of subjects with each severity will be presented by visit and by sign/symptom. Additionally, the shifts from baseline in irritation score will be tabulated by treatment, symptoms and scheduled post-baseline visits. The denominator for the proportions will be the number of subjects with any assessment of the sign/symptom both at baseline and at given visit.

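### Local irritation managed by a rest period between visits can be absent from the planned between-arm irritation and adverse event tables

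*Protocol*

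**What the plan says.** Protocol 6.3 sets a specific rule for this class of event. Irritation findings "are to be recorded only as AEs if they significantly worsen, require any medical intervention or result in subject discontinuation". The example attached to the rule is a grade 3 reaction that needs treatment.

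The same section then introduces the rest period: "Local irritation reactions in the treatment area are common and the Investigator may instruct Subjects to stop the application of treatment". On how it is ordered: "The Investigator may make this decision based upon a documented phone consultation or at an unscheduled visit". The interruption is recorded in the dosing log and compliance eCRF and in the subject diary.

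At an unscheduled visit where the subject stays in the study, Protocol 8.5 says that "required procedures at the discretion of Investigator considering the reason for visit will be performed". The Study Visit Schedule (Protocol section 4) nevertheless ticks the irritation evaluation in the unscheduled column.

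SAP 7.7.4 plans two irritation tables. For the first, "Number and percentage of subjects with each severity will be presented by visit and by sign/symptom". For the second, "the shifts from baseline in irritation score will be tabulated by treatment, symptoms and scheduled post-baseline visits".

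In SAP 7.7.1 the only AE category tied to action on study drug is "TEAE leading to discontinuation of the study medication". The same section plans a Fisher's exact test of Test against Reference for preferred terms above 1% in either group.

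**The concern.** The Synopsis gives the descriptive comparison of application site reactions a purpose: to check that the generic resembles the reference product on local tolerability. For a topical retinoid, a reaction strong enough to make the investigator stop the drug for some days is among the most informative tolerability events short of discontinuation.

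The rule for recording irritation as an AE passes over that event. The irritation tables rest on scores taken at three post-baseline scheduled visits, 28 days apart. If the reaction comes and goes between visits and is handled by phone, neither data stream need hold it, and the planned tables would not compare the arms on it.

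**Working it through.** The point rests on which data reach which table, so the main check is to follow one event through the plan. The documents give no figure here to reproduce.

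**The event.** A subject has irritation between two scheduled visits, the investigator orders a rest period, and the reaction has gone by the next scheduled visit.

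**Route 1: irritation score.**
- Scheduled visit: the score is taken on the day, and the reaction is no longer present.
- Phone consultation (allowed by Protocol 6.3): no score is taken.
- Unscheduled visit: the schedule calls for a score, while Protocol 8.5 leaves procedures to discretion. If a score is taken, it is outside the shift table in SAP 7.7.4. It may or may not be in the by-visit severity table, which is not expressly limited to scheduled visits. No worst post-baseline score is planned that would pick it up in any case.

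**Route 2: AE record.**
- Protocol 6.3 has three triggers: significant worsening, medical intervention, discontinuation. Interruption is not among them, and the first two are undefined.
- With no AE record, the event is outside all TEAE tables in SAP 7.7.1, including the Fisher test.
- With an AE record, it is counted under its preferred term, but no summary separates events that led to interruption.

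**Route 3: dosing data.**
- SAP 7.7.5 summarises compliance by treatment group, using missed doses. No breakdown by cause is visible, and parts of the section are redacted.

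Route 3 is therefore the only certain trace by arm, and it does not visibly identify irritation as the reason.

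**Illustration of how much a visit-day score can miss.** Inputs from the documents: scheduled post-baseline visits on Days 28, 56 and 84. Assumptions, because the documents give no onset or duration: one episode of d days, onset equally likely on each of Days 1 to 84, visits on their nominal days, and a score that reflects only the visit day.

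For d up to 28, each visit falls inside an episode for d of the 84 onset days, and the three sets do not overlap. So

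share touching a scheduled visit = 3d/84 = d/28; share touching none = 1 − d/28.

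| d (days) | Onset days touching a visit | Touching none |
|---|---|---|
| 3 | 9 of 84 | 89% |
| 5 | 15 of 84 | 82% |
| 7 | 21 of 84 | 75% |
| 10 | 30 of 84 | 64% |
| 14 | 42 of 84 | 50% |
| 21 | 63 of 84 | 25% |

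Onset matters too. If every episode began in Days 1 to 14, all those of up to 14 days would be missed, because the latest would end on Day 27 (14 + 14 − 1).

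**Effect on the comparison.** If a proportion p of an arm has one episode of d days, the proportion affected at any one visit is p × d/84. With the same d in both arms, the ratio of Test to Reference at a visit is (p_T × d/84)/(p_R × d/84) = p_T/p_R. The absolute difference shrinks by the factor d/84 and the ratio is kept. Only a difference in duration between arms distorts the ratio, and nothing in the documents gives its size or direction.

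**The case against.** The other side has five good arguments.

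1. **Protocol 5.1.4 directs the investigator to see the subject.** A reaction suggesting sensitivity or chemical irritation should be assessed promptly, at an unscheduled visit, and the schedule ticks irritation scoring there. Discretion under 8.5 is exercised in light of the reason for the visit, so a score is the natural procedure. This stands, and it narrows the gap. It does not close it, because 6.3 expressly permits the phone route for the rest-period decision.

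2. **The by-visit severity table may include unscheduled scores.** The SAP restricts only the shift table to scheduled visits. The table shells, which would settle this, are a separate document not available here. A reader might infer that the event is missing from every planned table, and the text does not support that. It can be missing, most clearly when managed by phone.

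3. **The AE triggers are broad.** An investigator could fairly regard stopping the drug as medical intervention, or the reaction as significantly worsened. The grade 3 text is only an example. Protocol 11.1 requires questions about AEs at each contact and adds that "All reported or observed signs and symptoms will be recorded individually". Some sites will record the event. But 6.3 is the specific rule for irritation, so sites may handle the same reaction differently.

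4. **Compliance is compared by arm.** An excess of interruptions in one arm could show in SAP 7.7.5. It would not visibly be attributed to irritation.

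5. **The direction of any bias is not established.** A reader might infer that rest periods lower visit-day scores more in the more irritating arm and so pull the tables towards similarity. That needs rest periods to shorten episodes unequally between arms. The documents give no durations, and with equal durations the ratio is preserved. It remains a possibility only.

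It can also be said that the comparison is descriptive and built around visits, and that nothing in the documents requires a worst-score table. That is true, and it is why this is offered as an improvement.

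**Conclusion.** The gap is real and limited. Protocol 6.3 does not name a rest period as an AE trigger and lets it be ordered without a scored assessment. The SAP plans neither a worst post-baseline score nor a summary of TEAEs leading to interruption. A rest-period reaction that resolves between Days 28, 56 and 84 can therefore escape the irritation and AE comparisons between arms.

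How often this would happen is unknown. The shares of 89% (3 days) down to 25% (21 days) apply to any short episode under visit-day scoring and rest on assumed onset and duration. They do not estimate how many rest-period reactions would be lost. One sentence in the rest-period paragraph of 6.3 and parts of SAP 7.7.5 are redacted. The reasoning uses only the visible text, chiefly Protocol 6.3 and SAP 7.7.1 and 7.7.4.

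This is a minor safety-reporting improvement. A reader should not carry it over to the equivalence or superiority analyses: the co-primary endpoints are lesion counts and are unaffected.

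**What to change.** Three changes:

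1. **Protocol 6.3.** Add a fourth AE trigger: irritation that leads the investigator to interrupt study drug (rest period).
2. **SAP 7.7.4.** Add a table, by treatment and by sign or symptom, of each subject's worst post-baseline score over all scheduled and unscheduled assessments.
3. **SAP 7.7.1.** Add TEAEs leading to interruption of study drug to the overall summary, and to the tables by system organ class and preferred term, so that irritation can be told apart from other causes.

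The cost is one phrase in the protocol, brief site training and a few descriptive outputs. The worst-score table uses scores already collected. Action taken on study drug is already required for each AE under Protocol 11.1, so the interruption summaries need no new field. The drawback is more AE records, for a reaction that the protocol itself expects to be frequent.
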